Rabies occurs throughout the year, and summer and autumn are the peak seasons for rabies in China (especially in August). In recent years, the distribution of rabies cases in China shows that 32% of the patients are children aged 14 and under, indicating that rabies is more harmful to children; 58% of the patients are 14-64 years old; and 10% of the patients are elderly people aged 65 and over.

The prevention of rabies depends on the awareness of rabies among susceptible populations to a large extent. The efforts to raise the awareness of rabies should include receiving rabies-related education, participating in activities organized by relevant agencies for the prevention of animal bites, and enhancing the sense of responsibility of dog owners and timely post-exposure disposal.

Based on the quantity of rabies vaccination in China, it is estimated that the annual number of people exposed to rabies virus in China exceeds 40 million. The surveillance on some provinces with a high incidence of rabies shows that more than 90% of the exposure seeking medical attention had Category II and Category III exposure, of which Category III exposure accounted for about 40%. About 10% of the people exposed to rabies virus failed to complete vaccination; only about 15% of people with Category III exposure received passive immunization biologics.

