9.5 Deviation From/Violation against the Protocol

Deviation from the protocol: refers to any behavior that does not conform to the clinical study protocol design or process and hasn't been approved by the Institutional Review Board. A behavior that does not affect the rights, safety and benefits of the subjects, or the integrity, accuracy and reliability of the study data and the evaluation of safety or main indexes should be deemed as a minor deviation from the protocol; a behavior that affects the rights, safety and

benefits of the subjects, or the integrity, accuracy and reliability of the study data and the evaluation of safety or main endpoints should be deemed as a serious deviation from the protocol (violation against the protocol).

It is unnecessary to report minor violation against the protocol (i.e., a deviation from the protocol), such as that the fifth dose of vaccine isn't injected within the window period, to the Institutional Review Board.

The on-site investigators should report to the principle investigator's unit, the Sponsor, the Institutional Review Board, and the Clinical Monitoring about the fact, process, cause, and impact of any serious deviation from the protocol (violation against the protocol) that occurs during the study process. The principal investigator and the Sponsor should give their opinions on the handling of such deviation.

The investigators should provide a corresponding training on relevant procedures to those personnel involved in any violation against the protocol in order to prevent similar incidents from happening again, and should record the training process.

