13.4 Analysis Set

As-Treated Population (Safety Population or Set)

Since post-exposure treatment of rabies is urgent and should not be delayed, randomization and prophylaxis will begin after a screening event that includes informed consent, urine pregnancy test and survey of inclusion criteria before some exclusion criteria have been confirmed. High-risk rabies exposure victims that meet all initially knowable inclusion/exclusion criteria will be randomized receive Study Drug and begin a regimen of rabies vaccination. All subjects who are randomized and receive Study Drug are included in the “as-treated” population.

Per-Protocol Population (Set)

All subjects who

- 1) randomized
- 2) receive the Study Drug
- 3) have inclusion/exclusion criteria confirmed
- 4) complete the rabies vaccinations schedule by Study Day 28
- 6) lack major protocol deviations
- 7) have adequate wound treatment and Study Drug injection of all exposure sites

will be included in the “per-protocol” population. Initial exclusion criteria that must be confirmed are the nature of the exposure including the species of the animal; a high risk exposure (WHO Category 3); interval ≤ 24 hours from the bite to the start of prophylaxis; the absence of RVNA ≥ 0.1 IU in serum obtained at Study Day 1, time “1” blood collection (WHO, 2013). Subjects who are discovered to not have satisfied criteria for the per-protocol population may be excluded from that population by the Per-protocol Adjudication Board.

* Inclusion/exclusion criteria to be confirmed include: Category III exposure to rabies virus <24 h; in the serum collected at "1" (WHO, 2013) on the first day of the study, the

RVNA<0.1 IU/mL.

In addition, subjects that have (not limited to) the following conditions may be removed from the PPS, which are subject to the result of discussion on the Blinded Data Review Meeting before the locking of database:

- Subjects will be excluded if there are conditions that may impair protection, such as immunodeficiency, after randomization.
- Subjects will be excluded if treatment is long-delayed (> 24 h).
- Subjects will be excluded if they receive or have received treatment prohibited by the protocol.
- Subjects will be excluded if the bite is not properly treated.

Per-protocol Adjudication Board (exclusion from the per-protocol population)

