2.2 Definitions of Analysis Sets

Safety Set (SS): includes all randomized subjects who have received at least 1 dose of study drug, used as the Safety Set of the study. Based on the SS, the subjects will be analyzed for safety by actual treatment groups; and be analyzed for demographic, baseline, and efficacy endpoints by planned groups.

Per-Protocol Set (PPS): includes all randomized subjects who have received correct study drug, have been confirmed for eligibility to inclusion/exclusion criteria*, have completed the rabies vaccination on Study Day 29 as required by the protocol, have no major protocol violations affecting the efficacy evaluation, and have received sufficient wound treatment at all exposed sites and received study drug injections.

* Inclusion/exclusion criteria to be confirmed include: Category III rabies exposure with a duration of <24 hours; RVNA <0.1 IU/mL in serum collected from blood sampling at time “0” on study day 1 (WHO, 2013). In our previous clinical study experience, about 2% to 5% of enrolled subjects may have the history of vaccination with rabies vaccine. Their RVNA response may be much quicker and higher than the naive patients. Since the RVNA is a critical efficacy endpoint, the subjects with a RVNA \geq 0.1 IU mL, which indicated the prior use of rabies vaccine, should be analyzed separately.

In addition, subjects with (not limited to) the following conditions will likely be excluded from the PPS, depending on the discussion at the blinded data review meeting prior to database lock:

- Subjects will be excluded for the conditions that may impair the protection (such as immunodeficiency) as discovered after randomization.
- Subjects will be excluded if excessive treatment delay (>24 hours) is discovered.
- Subjects will be excluded if they will receive or have received protocol prohibited treatments.
- Subjects will be excluded if all of the bite wounds are discovered to have not been properly treated or injected.

The primary analysis of the efficacy endpoints will be performed by the randomized groups of study drugs based on the PPS.

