3.2 Efficacy Analyses

Efficacy analyses will be performed based on the PPS and pre-defined SS, respectively, with the PPS used for the primary analysis and SS used for the supportive analysis. In case of any inconsistency between the actual and the pre-defined groups in the study, sensitivity analyses will be performed based on actual SS.

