3.2.2.3 AUEC₁₋₁₅ of RVNA GMC post-dose

The AUEC₁₋₁₅ of RVNA GMC will be calculated using the trapezoidal method. The primary analysis, subgroup analysis, and sensitivity analysis will be performed using the same method as that used for RVNA on Day 8 post-dose.

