3.4 Exploratory analysis

Considering that the current number of PPS subjects does not reach the sample size of AUEC₁₋₁₅ in the protocol for the hypothesis of superiority, and the RVNA before immunization in China clinical trial is limited by 0.5 IU/mL, the only reason for the inclusion of AUEC₁₋₁₅ analysis is that the PPS is excluded because the RVNA before immunization is ≥ 0.1 IU/mL and the RVNA before immunization is less than 0.5 IU/mL, and the exploratory analysis is performed on the subjects with the same analysis method as the RVNA on Day 8 after medication.

4 Interim Analysis

No interim analysis will be performed in this study. However, after all subjects have completed the safety and efficacy observations up to Day 99 post-dose (serology results on Days 1, 4, 8, 15, 43, 99 are available), the first analysis will be performed, and a statistical analysis report and a clinical study report will be drafted

and submitted to the NMPA for review. After all subjects have completed the safety and efficacy observations 1 year post-dose, a second analysis will be performed, and a statistical analysis report and a final clinical study report will be drafted and submitted to the NMPA as supplementary documents and submitted to the FDA US for review.

5 Modifications to Statistical Analysis Plan in the Study Protocol

“The difference in RVNA rates will also be analyzed using Wald” and “rate differences and P-values adjusted for stratification factor of study site will be calculated using the CMH method” are added in the SAP compared to the clinical study protocol (version: 2.0, 06-Dec-2020).

6 References

7 Appendices

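### The per-protocol set used for the Day 4, Day 8 and AUEC1-15 analyses depends on a vaccine dose due on Day 29, after the last sample for those endpoints

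*SAP*

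**What the plan says.** SAP 2.2 has a single PPS. Among other conditions, its members must "have completed the rabies vaccination on Study Day 29 as required by the protocol". The section closes with the rule that "The primary analysis of the efficacy endpoints will be performed by the randomized groups of study drugs based on the PPS". SAP 3.2 repeats the ranking, "with the PPS used for the primary analysis and SS used for the supportive analysis", where SS is the Safety Set. The Day 8 GMC (SAP 3.2.1.1), the Day 4 GMC (3.2.2.1) and AUEC1-15 (3.2.2.3, "performed using the same method as that used for RVNA on Day 8 post-dose") have no analysis set of their own. The only data rule tied to one PPS endpoint concerns late Day 99 samples (SAP 3.2.2).

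Protocol 13.4 has the same structure, but its vaccination condition is to "complete the rabies vaccinations schedule by Study Day 28". Protocol 11.6.2 schedules the fifth dose on Day 29 with a window of +2 days and moves later doses back if an earlier one is delayed. Protocol 9.5, giving an example of a minor deviation, writes "such as that the fifth dose of vaccine isn't injected within the window period".

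SAP 3.4 begins "Considering that the current number of PPS subjects does not reach the sample size of" AUEC1-15. It adds an exploratory analysis that brings back only subjects excluded solely because baseline RVNA was at least 0.1 but below 0.5 IU/mL.

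**The concern.** A per-protocol set should remove subjects whose conduct could distort the endpoint being analysed. A dose given or missed on Day 29 cannot change RVNA in serum drawn by Day 15. The same holds for the fourth dose, due at the Day 15 visit: protocol 11.10 times the Day 15 sample from the previous dose, so the same-day dose is not part of what that sample measures.

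For the primary endpoint and two secondary endpoints, membership therefore depends on behaviour after the outcome. Two things are at stake. First, the early comparisons are made in a group selected after the endpoint, for no gain in validity. Second, usable AUEC1-15 data can be left out of the primary analysis of the one endpoint for which the SAP reports too few subjects. SAP 3.4 returns subjects whose baseline RVNA, according to SAP 2.2, indicates earlier vaccination. It does not return baseline-eligible subjects whose only failing is a later dose.

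**Working it through.** **1. Timing.** Visit days and doses are from protocol 8.1.1, 8.1.3 and 11.6.2.

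| Endpoint | Last sample | Doses scheduled before that draw | Doses the PPS demands | Days from last sample to dose 5 |
|---|---|---|---|---|
| Day 4 GMC | Day 4 | 1 | 5 | 29 − 4 = 25 |
| Day 8 GMC | Day 8 | 1–2 | 5 | 29 − 8 = 21 |
| AUEC1-15 | Day 15 | 1–3 | 5 | 29 − 15 = 14 |

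**2. Reproducing the plan's AUEC1-15 figures.** Inputs (SAP 1.3.3, protocol 13.3): ratio 1.4755, margin 1.1, CV 142%, one-sided alpha 0.025, power 90%, allocation 3:1, dropout 20%.

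- Log-scale SD: σ = √ln(1 + 1.42²) = 1.0507
- Effect: δ = ln(1.4755/1.1) = 0.2937
- Control arm: n = (1 + 1/3)σ²(1.960 + 1.282)²/δ², which rounds up to 180. The total is 4 × 180 = 720 evaluable.
- With dropout: 720/0.8 = 900, as stated.
- Power with N evaluable: Φ(δ/(σ√(16/(3N))) − 1.960). At N = 1,000 this is 96.9%, as stated.

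The stated 96.9% thus assumes that all 1,000 are evaluable. With the plan's own 20% loss (800) power is 92.8%. A noncentral-t calculation agrees within about 0.1 percentage point over the range below.

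**3. AUEC1-15 power if subjects are returned to the PPS.** The documents give neither the PPS count nor the number excluded solely by the vaccination condition. Both are assumed here; 10 to 100 subjects is 1% to 10% of 1,000.

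| Assumed PPS | As is | +10 | +20 | +50 | +100 |
|---|---|---|---|---|---|
| 650 | 87.0% | 87.5% | 88.0% | 89.3% | 91.2% |
| 700 | 89.3% | 89.7% | 90.1% | 91.2% | 92.8% |
| 800 | 92.8% | 93.1% | 93.4% | 94.2% | 95.3% |

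**4. The shortfall in SAP 3.4.** The text does not say whether the target missed is 900 enrolled or 720 evaluable. Just under the first (899), power is still 95.2%. Just under the second (719), it is about 90%.

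**5. Day 4 and Day 8.** With only 400 evaluable (300 and 100):

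- Day 8: σ = √ln(1 + 1.205²) = 0.9471 and δ = ln(11.9/1.2) = 2.2942
- Day 4: σ = √ln(1 + 0.6325²) = 0.5801 and δ = ln(13.75/1.2) = 2.4387

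Power is about 100% for both. The issue there is selection after the endpoint, not precision.

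**6. The fifth-dose statements side by side.** Read literally, protocol 13.4 (by Day 28) excludes a subject who receives the dose on the scheduled Day 29. Protocol 11.6.2 allows Day 29 plus 2 days, and later still if an earlier dose slipped. Protocol 9.5 treats a dose outside the window as minor. SAP 2.2 names Day 29, qualified by what the protocol requires. These cannot all define the same set.

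**The case against.** **The data are not lost.** SAP 2.2 and 3.2 and protocol 13.4 and 13.5.3 analyse efficacy in the Safety Set as well, so subjects who miss dose 4 or 5 still appear for every early endpoint, and a large selection effect could show as a gap between the two sets. This stands as partial mitigation. The Safety Set does not decide the tests, and it also includes subjects with baseline RVNA of 0.1 IU/mL or more, so a gap could have another cause.

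**The rule may exclude few subjects.** Vaccine is supplied by the sponsor and given at scheduled visits, investigators are told not to suspend it (protocol 9.4.2), and protocol 13.4 says the adjudication board may, not must, exclude. This also stands: the number could be close to zero.

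Several stronger readings are tempting, and the documents do not support them:

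- *That the Day 29 condition caused the AUEC1-15 shortfall.* SAP 3.4 does not say so. The only exclusion it names is baseline RVNA.
- *That about 100 subjects are lost.* Protocol 5.1 does say "About 10% of the people exposed to rabies virus failed to complete vaccination", but this describes exposed people in China generally, not followed trial subjects. It can serve only as the upper end of an assumed range.
- *That the comparison is biased between arms.* Both arms receive the same vaccine, and nothing in the documents indicates that withdrawal before Day 29 differs by arm. Bias would need non-completion to be related to both arm and RVNA.
- *That a late fifth dose certainly removes a subject.* Taken with protocol 9.5 and 11.6.2, and with the blinded classification of deviations in SAP 3.1.2, the SAP wording can be read to keep that subject. A missed dose is the clearer case.

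**Conclusion.** The concern holds as a defect in the definition of the analysis set. One PPS requiring the full vaccine schedule is primary for endpoints whose last samples precede the fifth dose by 14 to 25 days, so subjects with valid samples can be excluded for a reason that cannot affect the endpoint.

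The size is unknown and probably modest. Under the plan's own effect and CV, and an assumed PPS of 700, returning 10 to 100 subjects takes AUEC1-15 power from 89.3% to between 89.7% and 92.8%. That matters mainly if the PPS is near the 720 needed for 90% power. AUEC1-15 is also last in the testing sequence (SAP 2.4). The Day 4 and Day 8 conclusions are not at risk for power. The conflicting fifth-dose statements need reconciling whatever the number affected.

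**What to change.** In SAP 2.2 and protocol 13.4, make the vaccination criterion specific to the endpoint, for analysis-set membership only and with no change to treatment:

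- Day 4: dose 1
- Day 8: doses 1–2
- Day 15 and AUEC1-15: doses 1–3
- Day 43 and later: the full-schedule condition, as now

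Report the full-schedule PPS as a sensitivity analysis for the early endpoints. List the change in SAP section 5.

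Reconcile the fifth-dose statements in protocol 9.5, 11.6.2 and 13.4 and SAP 2.2, so that it is clear which subjects meet the full-schedule condition.

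The programming cost is small: revised wording, one population flag per endpoint, and numbers analysed that vary by visit. The larger cost is procedural. SAP 3.4 suggests that the PPS had already been counted, so the record must show that the change was made blinded and before database lock. If that cannot be shown, keep the present PPS as primary and report the endpoint-specific sets as sensitivity analyses.

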2.3 Data Handling Principles

2.3.1 Baseline Definition

Unless otherwise specified, baseline is defined as the results of the last non-missing test or evaluation prior to the injection of investigational product. Change from baseline is defined as the observed value at this visit minus baseline.

2.3.2 Definition of the Number of Study Days

The number of study days will be calculated with the study start date, and will be used to indicate the time interval between the assessments of vital signs, adverse events, and concomitant medications during the study.

The start date of the study is defined as the injection date of investigational product.

If the date of examination or event is after the injection date of investigational product, then study day will be calculated as: Study Day = date of event - study start date +1.

If the date of examination or event is before the injection date of investigational product, then study day will be calculated as: Study Day = date of event - study start date.

2.3.3 Definition of Analysis Window

Data analysis will be performed based on the data directly collected at the visits, with no analysis window.

2.3.4 Handling Rules of Missing Data

Missing data are not planned to be handled in this study, unless otherwise specified.

2.3.4.1 Date of Adverse Event

Start dates of the AEs will be imputed as follows:

- If the entire start date of an AE is missing, the date will be imputed as the study start date (the date when the subject received the investigational product);
- If the year and month are available and are equal to the year and month of the study start date, the date will be imputed as the study start date if the AE end date (including the imputed date) is on or after the study start date, or the entire end date of an AE is missing; and the date will be imputed as the AE end date if the end date (including the imputed date) is before the study start date;
- If the year and month are available, but are not equal to the year and month of the study start date, the date will be imputed as the 1st day of that month;
- If the year is available and is equal to the year of the study start date, the date will be imputed as the study start date if the AE end date (including the imputed date) is on or after the study start date, or the entire end date of an AE is missing; and the date will be imputed as the AE end date if the end date (including the imputed date) is before the study start date;
- If only the year is available, but is not equal to the year of the study start date, the date will be imputed as January 1 of that year.

End dates of the AEs will be imputed as follows:

- If the year and month are available, the date will be imputed as the last day of that month;

- If only the year is available, the date will be imputed as December 31 of that year;

For died subjects, the AE end date should be imputed as the death date if the imputed AE end date is after the death date; for survived subjects at the end of study, the AE end date should be imputed as the study end date if the imputed AE end date is after the study end date.

2.3.5 Handling of RVNA Data Below the Lower Limit of Quantitation (BLQ)

For BLQs of RVNA data, they will be calculated as zero if the samples are collected prior to the injection date of investigational product, otherwise, they will be treated as missing data and will not be included in the analysis.

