11.3 Screening

Investigators should inquire about relevant information in accordance with the "inclusion and exclusion criteria", learn about each patient's medical history (including history of exposure to rabies virus, diseases/concomitant diseases and allergy, etc.), vaccination history and other medications, and carry out examination of vital signs (axillary temperature, pulse and blood pressure) and physical examination, including height, weight, overall skin conditions and skin condition at the wound. Female subjects should be required to collect urine samples for urine pregnancy test, which must be completed prior to blood sample collection on the day of vaccination. Investigators should fill relevant information about selection and demographic data (such as birth date, gender, and ethnicity) in the "Vaccination and Follow-up Records". Eligible patients should enter the next study procedure, and those ineligible patients should receive the injection of a RIG and/or a rabies vaccine at their own expense in accordance with routine clinical procedures.

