11.5 Blood Sampling Prior to Dosing

All subjects should be tested on the activity of rabies virus neutralizing antibodies. Approximately 3.0 mL of venous blood should be sampled prior to administrate the study drug and the first dose of vaccine, and serum should be aliquoted into two microtubes (one for testing, containing at least 0.5 mL of serum, while another is the backup), which should be stored at -20 °C or below.

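### SAP 2.3.5 ties the pre-dose BLQ rule to the injection date, so a BLQ result from the Day 1 pre-dose sample becomes missing and AUEC1-15 loses its starting point

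*SAP*

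**What the plan says.** SAP 2.3.5 has two branches for a BLQ result. In the first, "they will be calculated as zero if the samples are collected prior to the injection date of investigational product". In the second, "otherwise, they will be treated as missing data and will not be included in the analysis".

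The timing of the baseline sample is fixed elsewhere:

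- The protocol's study process table has one RVNA sample before dosing, at V1 (D1). Study drug is given at the same visit.
- Protocol 11.3 requires a urine pregnancy test of female subjects, "which must be completed prior to blood sample collection on the day of vaccination".
- Protocol 11.5: "Approximately 3.0 mL of venous blood should be sampled prior to administrate the study drug and the first dose of vaccine".
- SAP 2.3.2: "The start date of the study is defined as the injection date of investigational product".

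SAP 2.3.1 defines baseline differently from 2.3.5. It takes the latest available result before the injection, not before the injection date.

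The Day 1 value is used in AUEC1-15 (SAP 3.2.2.3: "RVNA GMC will be calculated using the trapezoidal method"), in the Day 1 RVNA grouping at 0.1 IU/mL (baseline characteristics in SAP 3.1.3, Safety Set subgroup in SAP 3.2.1.1.2), and in the RVNA criterion for the Per-Protocol Set (SAP 2.2). SAP 2.3.4 plans no handling of missing data unless otherwise specified.

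**The concern.** A SAP is programmed from its text. A program that compares the sample date with the injection date finds them equal on Day 1. The condition for zero fails and the value goes to the missing branch. No scheduled sample would ever meet the condition, short of a visit that runs past midnight.

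A BLQ result is a natural baseline for a person without earlier rabies vaccination, so the rule could remove the Day 1 value from the population the trial is about. AUEC1-15 needs that value for its first trapezoid, and the SAP gives no fallback. Someone would have to decide between dropping the subject and starting the area at Day 4, and the plan does not say which. AUEC1-15 is formally tested (SAP 2.4) and drives the largest sample size (SAP 1.3.3).

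**Working it through.** **1. Date logic.** Sample date = Day 1 = injection date. The test of whether the sample precedes the injection date is false, so the BLQ value is missing. Under SAP 2.3.1 the same sample is before the injection and would be the baseline. The two sections disagree.

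**2. The plan's AUEC1-15 figures (SAP 1.3.3).** Ratio 1.4755, margin 1.1, CV 142%, one-sided 0.025, power 90%, allocation 3:1, dropout 20%.

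- SD on the log scale = √ln(1 + 1.42²) = 1.0507
- Difference = ln(1.4755/1.1) = 0.2937
- Control n = 1.0507² × (1 + 1/3) × (1.960 + 1.282)² / 0.2937² ≈ 179.3, so 180; total 720; 720/0.8 = 900, as stated
- With 750 + 250: SE = 1.0507 × √(1/750 + 1/250) = 0.0767; power = Φ(0.2937/0.0767 − 1.96) = 96.9%, as stated

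The 96.9% assumes that all 1,000 subjects are evaluable. With 800 it is 92.8%.

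**3. If the area starts at Day 4.** With samples on Days 1, 4, 8 and 15, the area is 1.5(C1 + C4) + 2(C4 + C8) + 3.5(C8 + C15). The first term is lost.

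Inputs for SYN023 (Days 4 and 15 as ranges):

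- Day 4: 2 to 4 IU/mL, an assumption.
- Day 8: 4.55 IU/mL, the Day 7 post-dose mean in the arm without vaccine (Protocol 6.3.4).
- Day 15: 53.27 IU/mL, the Day 14 post-dose mean in the vaccine arm of the same study (SD 52.66). The matching log-normal geometric mean is 53.27/√(1 + (52.66/53.27)²) ≈ 38. A low case of 10 is an assumption.

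For HRIG I divide by the SAP's ratios, 13.75 on Day 4 and 11.9 on Day 8, and set Day 15 so that the full-area ratio is 1.4755.

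Example with Day 4 = 4 and Day 15 = 38:

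- SYN023 area = 6 + 17.1 + 148.925 = 172.025; HRIG area = 172.025/1.4755 = 116.588
- First trapezoid: SYN023 6.000 (3.5%); HRIG 1.5 × 4/13.75 = 0.436 (0.4%)
- Ratio from Day 4 = 166.025/116.151 = 1.429
- Power = Φ(ln(1.429/1.1)/0.0767 − 1.96) = 92.7%

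| SYN023 Day 15 | SYN023 Day 4 | Ratio from Day 4 | Power, 1,000 subjects |
|---|---|---|---|
| 53.27 | 2 | 1.457 | 95.6% |
| 53.27 | 4 | 1.440 | 94.0% |
| 38 | 2 | 1.451 | 95.1% |
| 38 | 4 | 1.429 | 92.7% |
| 10 | 2 | 1.416 | 90.9% |
| 10 | 4 | 1.368 | 81.0% |

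The lost piece is small, but it is where the arms differ most, so nearly all of the loss falls on SYN023.

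**4. If AUEC1-15 is set to missing.** Only subjects with a quantifiable baseline remain. SAP 2.2 expects 2% to 5% to have a vaccination history. If only they were quantifiable (an assumption), 20 to 50 of 1,000 would remain, with power of about 8% to 13%. The Per-Protocol Set excludes RVNA of 0.1 IU/mL or more, so if the LLOQ is near 0.1 it would keep almost nobody for this endpoint.

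**5. Does the substituted value matter?** With Day 4 at 3 to 4.5 and Day 15 at 10 to 53.27 IU/mL, a Day 1 value of 0.05 or 0.1 instead of 0 in both arms moves the ratio by no more than about 0.002. Only missing versus present matters.

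**The case against.** The best defence is that the intent is obvious. A zero branch that applies to no scheduled sample has no purpose, SAP 2.3.1 refers to the injection itself, and SAP 1.3.1 separates pre-dose from post-dose samples. A careful programmer would set the Day 1 BLQ value to zero. I accept that as the intent. It does not remove the need to correct the text, because the literal rule gives a different result and the SAP does not say which section prevails.

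The reach is also limited, and this stands. The Day 8 model has only treatment and site (SAP 3.2.1.1.1). The Day 4, Day 99 GMC and Day 99 positivity tests do not use the Day 1 value as an analysis variable. AUEC1-15 is last in the hierarchy, so its failure blocks no other test. Starting at Day 4 moves the ratio towards the null: the cost is power, not a false claim of superiority.

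A reader might go further and infer two things that the documents do not support.

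- *That every rabies-naive subject loses the baseline.* SAP 2.2 takes RVNA of 0.1 IU/mL or more as a sign of earlier vaccine. It does not equate naive with BLQ, and no LLOQ is stated.
- *That the per-protocol check fails.* SAP 2.2 asks that subjects "have been confirmed for eligibility to inclusion/exclusion criteria", but this is settled at blinded data review and by the adjudication board on screening data (Protocol 13.4). The protocol words the criterion as absence of RVNA at or above 0.1. A reported result below an LLOQ of 0.1 or less meets it. Nothing says that the check uses the BLQ-handled variable, and SAP 3.4 shows baseline RVNA already sorting subjects for that set.

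**Conclusion.** The rule is wrong as written. A Day 1 pre-dose BLQ result becomes missing, against SAP 2.3.1 and the rule's own evident purpose. The tested endpoint at risk is AUEC1-15. Under the literal rule its power falls from 96.9% to about 93% to 96% with 1,000 subjects if the area starts at Day 4 (Day 4 at 2 to 4, Day 15 at 38 to 53 IU/mL), and to 81% to 91% if Day 15 is near 10. If the endpoint is set to missing, it could nearly collapse. These figures treat every baseline as BLQ and rest on assumed titres. With few BLQ baselines the effect would be small. There is little slack, since SAP 3.4 says that the Per-Protocol Set already falls short of the AUEC1-15 sample size.

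The Day 1 grouping in the baseline tables and the Safety Set subgroup carries the same risk if it is programmed from the BLQ-handled value. Harm to the Per-Protocol Set is not established, and the primary Day 8 result is untouched. Severity: minor to moderate, because harm requires literal programming and reaches one tested endpoint.

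**What to change.** In SAP 2.3.5, make the zero branch apply to samples collected before the injection of investigational product, by date and time, and name the Day 1 pre-dose sample explicitly. Then add that a pre-dose BLQ result:

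- enters AUEC1-15 as zero; and
- counts as below 0.1 IU/mL for the Day 1 grouping and the per-protocol criterion, provided that the LLOQ is 0.1 IU/mL or less. State the LLOQ.

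Also say how AUEC1-15 is handled when the Day 1 sample was truly not obtained.

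The cost is a few sentences in the SAP. No design or data-collection change is needed: time of administration is already listed (SAP 3.3.1), and the sample can be identified by its scheduled visit.
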